#### **4. Design & Procedures:**

This study will be a prospective, uncontrolled clinical trial. The study will not be controlled as invasive monitoring of hemodynamics will be performed, allowing clear demonstration of a cause-effect relationship.

This study aims to piggy-back on an elective right heart catheterization (RHC) in subjects with chronic heart failure. The right heart catheterization will be part of the subject's standard of clinical care (SOC). Subjects eligible for this study will be referred to the Duke cath lab for the evaluation of cardiac filling pressures because it is found to be necessary by the outpatient provider. This will occur in the cardiac catheterization lab. Subjects get scheduled for RHC days to weeks (2-3) ahead of their procedure. The eligible subject will be contacted before the study to be informed about the eligibility for the study and basic information about the study will be provided over the phone shortly after they have been scheduled. Subject will be consented in person in the morning of the procedure.

The subject will undergo pre procedural testing as demonstrated below in the flow chart (all part of the clinical study - CS). Besides the RHC (SOC) the subject will undergo an invasive cardiopulmonary exercise with the RHC in place. Baseline evaluation is followed by a regional nerve block (bilateral splanchnic nerves) while the subject is in the catheterization lab. This will be performed by an anesthesiologist experienced in splanchnic nerve blocks.

Figure 2: Study flow chart

[figure not shown]

Table: Study events

Required Assessment	Pre procedure (day of)	Baseline (intra-procedure)	Block	Post Block Procedure	Recovery	24 h after procedure	48 h after procedure	6 Months after Procedure (±14 days)
Vitals (BP, HR, RR, SpO2)	X (SOC)	X (SOC)	X (SOC)	X (SOC)	X (SOC)			
Weight	X (SOC)				X (SOC)			
Orthostatic vitals	X (CS)				X (CS)			
Urine output (continuous recording)	X (CS)	X (CS)	X (CS)	X (CS)	X (CS)			
Valsalva		X (CS)		X (CS)				
Labs: BMP, pro-BNP, urine sodium,	X (SOC/CS)				X (CS)			
Labs (Angiotensin II), Plasma Metanephrines, Vasopressin, Plasma Catecholamines, Lactate		X (CS)		X (CS)				
Dyspnea Questionnaire		X (CS)		X (CS)	X (CS)	X (CS)	X (CS)	
Six minute walk test	X (CS)				X (CS)			
Impedance and lung fluid content measurement		X (CS)		X (CS)				
Heart rate variability	X (CS)	X (CS)	X (CS)	X (CS)	X (CS)			
Echocardiogram		X (CS)		X (CS)				
Invasive CPX		X (SOC/CS)		X (CS)				

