2. Unilateral splanchnic nerve block performed by an anesthesiologist (see images below) (CS). The anesthesiologist will perform a unilateral block to the splanchnic nerve. The blood pressure will be checked, after 15 minutes, post-block. If the systolic blood pressure is reduced by  $> 20$ mmHg, the contralateral splanchnic nerve will not be blocked. Following the right heart catheterization procedure the subject will be prone on the abdomen. Central venous access remains in place. Needle will be placed under fluoroscopic guidance in the posterior chest wall. Anesthetic solution (1.5% lidocaine with 1:200,000 epinephrine and of 0.5% ropivacaine) will be injected. Lidocaine 1.5% with Epinephrine 1:200,000 will be used initially to confirm extravascular administration. The subject will then be placed back on his/her back. The subject will then undergo repeat hemodynamic measurement with the RHC catheter that was already in place. Then the subject proceeds with invasive cardiopulmonary testing after a 30 minute break. The central venous catheter will be removed after the hemodynamic monitoring/testing is completed in the catheterization laboratory.

Additional measurements include:

- Orthostatic vitals (CS).
- Dyspnea questionnaire (CS)
- Echocardiography and liver flow measurements (CS)

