#### Blood samples processing:

Some blood samples collected before and after the nerve block (plasma metanephrines, plasma catecholamines, angiotensin II and arginine vasopressin, lactate) will be processed (centrifuged) and stored at -70 degrees Fahrenheit before sent out to an external lab. Storage

duration may vary between weeks to months. Samples will be stored in a research freezer located on the 7th floor of Duke North (cath lab research freezer). As part of the study, we will send blood for study-related laboratory tests to the Mayo clinic and Inter Science Institute. These would include laboratory tests such as metanephrines, vasopressin, catecholamines, and angiotensin. A data transfer agreement is already in place.

Safety endpoints:

- The duration of the anesthetic block is estimated for 12-24 hours. The subject will be monitored for up to 3 hours in the catheterization laboratory/holding area, if there is any concern or evidence of procedure related complications the will be kept overnight in the cath lab holding area. A potentially observed effect of the block to prevent discharge the day of procedure could be orthostatic hypotension. will also be contacted at 48 hours post procedure to ascertain any potentially missed complications. Further the subject's medical chart will be observed for 6 months following study enrollment to evaluate for admissions for heart failure.

Incidence of major side effects has been reported to be <1:1000 and are expected to occur immediately post nerve block. They include:

- Pneumothorax, possibly requiring a chest tube
- Aortic puncture with retroperitoneal bleed or hemothorax
- Spinal cord trauma with possibly paralysis

Incidence of minor side effects like:

- Orthostatic hypotension
- Pain at puncture site and intercostal neuralgia
- Gastrointestinal dysmotility including diarrhea, constipation and abdominal cramping
- Bleeding at puncture site

Efficacy endpoints:

The following efficacy endpoints will be evaluated:

- Primary:
- Improvement in 20 W and peak exercise PA mean and wedge pressure
  - Reduction in central venous pressure and/or pulmonary artery pressure (diastolic) and/or pulmonary capillary wedge pressure at 30 minutes after nerve block

Secondary:

- Reduction in central venous pressure and/or pulmonary artery pressure (diastolic) and/or pulmonary capillary wedge pressure at 30 minutes after nerve block

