### **14. Data Analysis & Statistical Considerations:**

Descriptive statistics of continuous outcomes will include sample size, mean, median, standard deviation, minimum and maximum. For categorical outcomes, the number and percentage of subjects in each category will be presented. Statistical comparisons will be made using t-tests for continuous outcomes and chi square or Fisher's exact test (depending on overall event rates) for categorical outcomes. Paired t-tests will be used to compare changes from baseline to post-intervention. All statistical analyses will be performed using SAS for Windows (version 8.2 or higher) or other widely accepted statistical or graphical software. Subject data listings and tabular and graphical presentations of results will be provided. Unless otherwise specified, a two-sided 0.05 level of significance will be used to declare change in pre- and post-procedure variables different.

For power analysis, our primary endpoint is decreased in central venous pressure following nerve blockade. Based on preliminary animal experiments, we anticipate a reduction of CVP of 25%. For a sample size of 16, If the true difference in the experimental and control means is 25%, we will be able to reject the null hypothesis that the population means of the experimental and control groups are equal with probability (power) .90. The Type I error probability associated with this test of this null hypothesis is 0.05.

There is no direct measure of technical success following attempted block of the splanchnic nerves. The location of the splanchnic nerves is estimated biased on human anatomy dissections and established nerve block protocols used by the anesthesiology department. Procedural success to block the splanchnic nerves will be assumed in 70% of the cases based on the experience in splanchnic nerve blocks in subjects with intractable cancer.

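### Section 14's power of .90 at n=16 for a 25% CVP fall does not apply the plan's own 70% block success; if 25% is per successful block and failures have no effect, power is about 0.56-0.62 at 16 and 0.85-0.90 at 30

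*Combined protocol and SAP*

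**What the plan says.** Section 14 (Data Analysis & Statistical Considerations) contains the plan's only power calculation. The effect size is introduced with "Based on preliminary animal experiments, we anticipate a reduction of CVP of 25" percent. The power statement is conditional: "For a sample size of 16, If the true difference in the experimental and control means is 25" percent, the null hypothesis is rejected with power .90 at a type I error of 0.05. No standard deviation is given.

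The following paragraph turns to the procedure. It says "There is no direct measure of technical success following attempted block of the splanchnic nerves", and then "Procedural success to block the splanchnic nerves will be assumed in 70% of the cases", citing experience with these blocks in cancer patients.

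On the analysis, the same section says "Paired t-tests will be used to compare changes from baseline to post-intervention", at a two-sided 0.05 level unless otherwise specified. Nothing excludes subjects whose block failed.

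Section 4 describes the trial as uncontrolled. Section 7 sets enrolment at up to 30 subjects, 15 in each of two heart failure types. Under Section 9 a subject counts as enrolled at consent, which comes before the hemodynamic checks in Sections 4 and 7 that can stop a subject from being blocked.

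**The concern.** The two paragraphs of Section 14 describe different things. One gives the power for a 25% mean fall in CVP. The other says that about three blocks in ten are expected to fail and that nobody will know directly which ones. If the 25% describes a nerve that has actually been interrupted, the mean change over everyone analysed will be smaller, because the failed blocks cannot be removed. Mixing successes and failures also adds spread to the changes.

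The text does not say which kind of effect the 25% is, but its source points one way. The only animal work on nerve interruption that Section 3 describes is surgical transection of the splanchnic nerve, which is complete interruption and has no counterpart to a missed block. On that reading, .90 at 16 does not describe the analysis the plan will run. At stake is whether the plan's single power figure can be relied on, particularly if the number of blocked subjects ends well short of 30.

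**Working it through.** **Inputs.** From Section 14: n = 16, difference 25 percentage points of CVP, power 0.90, alpha 0.05 two-sided, paired t-test, success 70%. From Section 7: up to 30 subjects. Because the trial is uncontrolled and the test is paired, I read the experimental and control means as the post-block and pre-block means of the same subjects.

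**Step 1: the plan's own figure.** Without an SD, .90 cannot be checked independently, only inverted. With the noncentral t distribution (15 degrees of freedom, noncentrality d x sqrt(16)), power 0.90 requires d = 0.868. The implied SD of change is 25 / 0.868 = 28.8 points. By construction, this SD with a 25-point mean returns .90 at 16.

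**Step 2: dilution.** Assume 25 is the effect of a successful block and a failed block has none.
- Mean over attempted blocks: 0.70 x 25 + 0.30 x 0 = 17.5 points.
- SD if the mixing of successes and failures is ignored: 28.8, so d = 17.5 / 28.8 = 0.61.
- SD with the mixture, taking the same within-group SD in successes and failures: sqrt(28.8² + 0.70 x 0.30 x 25²) = sqrt(829.4 + 131.3) = 31.0, so d = 17.5 / 31.0 = 0.56.

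**Step 3: power** (two-sided paired t, noncentral t).

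| Blocked subjects | Mixture SD 31.0 | SD unchanged 28.8 |
|---|---|---|
| 16 | 0.56 | 0.62 |
| 20 | 0.67 | 0.73 |
| 24 | 0.75 | 0.81 |
| 30 | 0.85 | 0.90 |

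Simulating the mixture with 200,000 replicates gives 0.56 at 16 and 0.85 at 30, in agreement with the formula. About 31 (SD unchanged) to 35 (mixture) blocked subjects would be needed for 0.90.

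**Step 4: a check that does not use the back-solved SD.** Power 0.90 needs d = 0.868 at n = 16 and d = 0.612 at n = 30. With a mean of 17.5, the largest SD of change that still gives 0.90 is:
- n = 16: 17.5 / 0.868 = 20.2 with no mixture term; as a within-group SD under the mixture, sqrt(20.2² - 131.3) = 16.6.
- n = 30: 17.5 / 0.612 = 28.6; under the mixture, sqrt(28.6² - 131.3) = 26.2.

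So under the successful-block reading, .90 at 16 requires an SD of at most about 17 to 20 points, against the 28.8 that the plan's sentence implies.

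**Step 5: the other reading.** If 25 is already the mean over attempted blocks, nothing is diluted and .90 at 16 stands. With no effect in failures, a successful block would then have to lower CVP by 25 / 0.70 = 35.7%.

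**The case against.** The strongest reply is that the sentence is correct as worded. It conditions on a true difference in means of 25%, which can be read as the mean in the population tested, failures included. The animal experiments behind the figure are not described, so the documents cannot settle which effect it is. This stands, and it is why the point is conditional.

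Second, the fall at 16 is partly built in. The SD was solved from .90 at 16, so any dilution must lower power there. That also stands. Step 4 avoids the back-solved SD but shows only which SDs would preserve .90, not what the true SD is.

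Third, the plan aims for up to 30 subjects, not 16, and the worst case computed above is still 0.85 at 30. Falling to about 16 would mean losing nearly half of the 30. The documents allow losses after consent but give no rate and no minimum number.

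Fourth, the range is not a bound. It assumes equal within-group variation in successes and failures and no effect in failures. If failed blocks showed no variation at all, power at 16 would be 0.69-0.72. If failures kept part of the effect the loss would be smaller, but nothing in the documents supports a particular share.

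A reader might go further and infer that .90 is simply wrong or that the trial is underpowered. The documents do not support that: no SD is given, the 25% may already average over attempted blocks, and at 30 blocked subjects the loss is small.

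**Conclusion.** The point holds as a conditional one, of minor severity. What is certain is the omission: the power statement does not use the 70% success stated in the next paragraph, and the kind of effect meant by 25% is not defined. The size of the consequence rests on four assumptions: that 25% is the effect of a successful block (likelier, but an inference from the transection work in Section 3); that failed blocks have no effect; that the SD of change is the back-solved 28.8 points; and, for the lower ends of the ranges, that within-group variation is the same in successes and failures. Under these, power is about 0.56-0.62 at 16 and 0.85-0.90 at 30 blocked subjects, instead of .90 at 16. Under the attempted-block reading there is no shortfall. CVP is taken as the powered endpoint because Section 14 names it; how that sits with the primary endpoints listed in Section 4 is a separate question.

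**What to change.** Replace the power sentence in Section 14 with one of this form: *With [N] subjects expected to be blocked, a two-sided 0.05 paired t-test has power [X] to detect a mean change of [M] over all attempted blocks, assuming an SD of change of [S] (source: [ ]). Every subject with an attempted block is analysed, whatever its presumed success.*

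Then state where M comes from:
- If 25% is the effect of a successful block, use M = 0.70 x 25% = 17.5%, say that no effect is assumed in failed blocks, and widen S to sqrt([within-group SD]² + 0.21 x 25²).
- If 25% is already the average over attempted blocks, say so, enter it as it stands, and do not apply the 70% again. The same applies to any mean taken from the human pilot in Section 3, which would average over attempted blocks.

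Take X from the sourced S, not from the 28.8 points back-solved here. N should allow for subjects who consent but are not blocked.

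The cost is a few sentences. The printed power may fall below .90, and under the first option the no-effect assumption cannot be checked directly, since block success is not measured. No extra patients, visits or procedures are needed.

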### **15. Data & Safety Monitoring:**

Due to the experimental nature of this intervention, data will be recorded after each subject completes the intervention for signs of unintended negative effects. These include hypotension, worsening renal function, or clinical deterioration. Additionally, subject's electronic medical data will be screened for any traumatic complications from the nerve block at 48 hours post-procedure.

Unanticipated adverse events, which are severe (listed above), will be reported to the IRB within 24 hours. Any other adverse event will be reported to IRB within 10 working days or per IRB policy. The Principal Investigator will also provide an annual report of any side effects or problems to the IRB during the study renewal process.

Following discharge, the subject's medical record will be monitored for readmission to the Duke hospital for heart failure for 6 months.

No PHI is sent outside of Duke.

16. **Privacy, Data Storage & Confidentiality** – see Section 12 of the e-IRB submission form and complete the questions in that section.

1. Data will be obtained by approved study personnel. An enrollment log will also be maintained in Excel Spreadsheet on the Heart Center's S:drive. The subject ID will also be stored on the folder to track subject enrollment and collection of data. Data will be recorded in Excel. Only deidentified data will be available for statistical analysis. All subject identifiers will be removed for database storage, statistical analysis and data reporting. This data will be stored on a study specific folder on the Duke server behind the Duke firewall. The subject ID code will be destroyed after data analysis is completed. Protected health information will not be used for any other purposes than those described in this protocol without obtaining further IRB approval. This information will be used for research purposes only and subjects will never be contacted regarding information obtained through chart review. A designated statistician from the DCRI will provide support with statistical analysis.

The adequacy of the Research Data Security Plan (RDSP) will be evaluated and approved by the Cardiology CRU prior to study conduct.

Any publications or presentations that result from this research will not identify any subjects individually, and will present data in aggregate form only.

Gathered data will be stored for at least 6 years.
